3.3. Research population

The target population in this study were: (1) patients with coronary heart disease who indicated coronary artery bypass surgery (CABG) and off pump coronary artery bypass (OPCAB), (2) patients who had heart valve disease indicated by open-valve heart surgery. The target population was patients who underwent adult cardiac surgery at the Division of Adult Cardiac Surgery, RSPJNHK, from October to December 2022.

3.4. Sample selection method

Sampling in this study was conducted consecutively, including all patients who underwent cardiac surgery in the Division of Adult Cardiac Surgery, RSPJNHK, until reaching the target sample size.

3.5. Inclusion, exclusion, and dropout criteria

3.5.1. Inclusion criteria

1. Adult patients aged ≥ 18 years
2. Coronary heart disease patients indicated for coronary artery bypass surgery and off-pump coronary artery bypass (OPCAB)
3. Patients with heart valve disease are indicated for aortic or mitral valve repair and replacement through open heart surgery.

4. The patient underwent open heart valve surgery with tricuspid valve repair.
5. Patients undergoing open heart surgery at the Adult Cardiac Surgery Division, RSPJNHK.

3.7.1. Exclusion criteria

1. Patients who expressed unwillingness to become research subjects.
2. Patients who have an allergy to tranexamic acid.
3. Patients were undergoing urgent/emergency surgery and minimally invasive surgery
4. The patient underwent a double procedure of simultaneous aortic and mitral valve surgery.
5. Patients with a history of bleeding disorders (coagulopathy) such as clotting factor deficiency and heparin-induced thrombocytopenia or use of intravenous anticoagulants other than heparin at the time of surgery.
6. Patients with a history of thromboembolic disease.
7. Patients with active Infective endocarditis
8. Patients with a history of previous cardiac surgery
9. Patients with a estimated glomerular filtration rate <30 mL/min or on dialysis
10. Patients who receiving oral therapy with clopidogrel, aspirin, dabigatran, or rivaroxaban in the last five days
11. Patients who receiving chronic warfarin therapy who have not stopped their medication and have an international normalized ratio (INR) >1.5 before surgery
12. Patients with pre-operative thrombocytopenia (<50,000 platelets per μ L)
13. Pregnancy or breast feeding patients
14. Patients who refusal of blood products
15. Patients with a pericarditis

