2.3. Tranexamic acid

6.3.1. Tranexamic acid pharmacology

Tranexamic acid is a synthetic compound derived from the amino acid lysine that is an analog of aminocaproic acid and acts as a fibrinolysis inhibitor. Tranexamic acid works by binding to the five binding sites of the amino acid lysine on plasminogen to inhibit its activation into plasmin which plays a role in fibrinolysis. To inhibit its activation into plasmin which plays a role in fibrinolysis. In addition, tranexamic acid also has an anti-inflammatory profile by inhibiting plasmin-mediated activation of complement, monocytes, and neutrophils. This drug has good absorption with oral administration, an initial dose of 15 mg/kg and a follow-up dose of 30 mg/kg every 6 hours, and is eliminated through the kidneys. Tranexamic acid can also be given intravenously at a dose of 0.5-1 gram three times per day with a dose restriction of 5-10 mg/kg in patients with renal failure.²⁹ The minimum concentration required to inhibit fibrinolysis in vitro is 10 mcg/ml in adults.³⁵ A meta-analysis conducted in 2020 said that tranexamic acid administration did not affect blood clotting time but significantly reduced post-surgical bleeding and transfusion requirements in patients with cardiac surgery.³⁶

This compound is widely used as a prophylactic and therapeutic agent for bleeding, for example, in surgical interventions and severe trauma, thus reducing the amount of perioperative bleeding and the blood products transfusion after cardiac surgery. Early administration of tranexamic acid, primarily via the intravenous route, is known to increase the chances of survival in emergency cases of massive bleeding. Due to its significant role,

the World Health Organization (WHO) included tranexamic acid in the list of essential drugs.³⁷ However, it is contraindicated in patients with disseminated intravascular coagulation and upper genitourinary tract bleeding (kidney and ureter) due to its potential to cause excessive blood clot formation.³⁴

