6.3.3. Comparison of systemic and topical tranexamic acid

Intravenous administration of tranexamic acid has been associated with an increased risk of thromboembolism and early *graft* closure in coronary artery bypass surgery. Reported cases of thromboembolism include cerebral, pulmonary, mesenteric, and retinal thromboembolism. Due to the significant systemic side effects of intravenous administration, topical administration of tranexamic acid has become increasingly popular. This is because the local antifibrinolytic effect facilitated by the topical application of tranexamic acid has proven effective in preventing bleeding in several other disease cases, such as post-oral surgery of patients with hemophilia, epistaxis, bladder surgery, and gynecological bleeding.⁵¹

Topical administration can provide adequate concentrations at the wound site while providing low systemic concentrations.³⁵ Other studies show that topical tranexamic acid in surgery can significantly reduce bleeding and transfusion requirements without increased side effects.^{52,53} This condition may be due to the shallow degree of systemic absorption after topical application compared to intravenous bolus administration. The study stated that topical application of tranexamic acid gave a mean peak serum concentration of 4.9 mcg/mL in the group treated with fluid bolus in the wound cavity and 5.2 mcg/mL in the group treated with moisturizing the wound surface. These levels are lower than the minimum levels required for systemic effects. In addition, at 5 mcg/mL, only 0.5 mcg/mL will cross the blood-brain barrier, making it very unlikely to cause seizures. In contrast, after administration of 1 g of intravenous tranexamic acid, the serum concentration is above 10 mcg/mL for about 2.5 hours.³⁵

Topical administration of tranexamic acid in surgery is generally given as a bolus to the cavity or added to irrigation fluid.³⁵ In a study by De Bonis et al.

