5.7. Data collection and retrieval steps

3.7.1. Before surgery

Patients with coronary heart disease and heart valve disease who were indicated for cardiac surgery were determined to be eligible for the study based on the inclusion and exclusion criteria through history taking, physical examination, and the results of supporting examinations (electrocardiography, cardiac enzymes, and laboratory) obtained from the

patient's medical record at RSPJNHK. Furthermore, researchers conducted *informed consent* to patients who were eligible to become research subjects and asked for written consent from patients. Patients who agreed to the *informed consent* were randomized into treatment or control (placebo) groups. A research assistant carried out randomization using the "randomizer.org" site. The treatment group in this study received 5 g of tranexamic acid in 50 mL of 0.9% NaCl solution administered topically to the pericardial cavity after protamine administration and before sternotomy closure. In contrast, the control group (placebo) received 100 mL of 0.9% NaCl solution without tranexamic acid administered in the same way as the treatment group. The pharmacy department prepared the preparations in the study so that neither the researchers nor the patients were aware of the preparations used intraoperatively.

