3.7.2. Perioperative

Patients who became research subjects underwent coronary artery bypass surgery according to standard operating procedures at RSPJNHK. After inducing anesthesia, undergoing sternotomy, and installing a heart-lung bypass machine (*on-pump*), the patient underwent the primary procedure. Then the research protocol was carried out with either treatment or control (placebo) after the heart-lung bypass machine stopped and before the sternum was closed by previously clamping the chest tube. After skin closure was completed, the chest tube clamps were reopened, and internal suction was performed, followed by connecting the chest tube with a *water-sealed drainage* system to accommodate post-surgical intrathoracic bleeding. The sternal closure to skin suturing process is done within 30-45 minutes.

In OPCAB group, after the graft anastomosis with OPCAB technique was completed, before sternal closure, the patient was given an intervention in

the form of topical tranexamic acid (5g/50mL) or placebo (50mL normal saline) dissolved in 100mL normal warm saline (37° C) which was inserted into the pericardial cavity including mediastinal tissue and allowed to stand for five minutes. It was then cleaned and sternal closure was performed.

The study subjects then underwent heart valve surgery according to the standard operating procedures of RSJPDHK, which began with induction of anesthesia, sternotomy, and CPB insertion. After the heart-lung bypass machine stopped, the chest tube was installed and clamped, the Subject then received one of the placebo or treatment fluids which were divided into two administrations, 50 mL of the first liquid was given to the intrapericardium and 50 mL of the second liquid was given to the sternum. The sternum was closed to the skin with an estimated completion of 30-45 minutes. Chest tube clamps were opened and connected to a water-sealed drainage (WSD) system to remove residual bleeding in the thorax after surgery.

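### The exclusion criteria leave out bleeding from the kidney or ureter, which the protocol itself names as a contraindication to tranexamic acid (small safety gap, one-line fix)

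*Combined protocol and SAP*

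**What the plan says.** Section 6.3.1 (Tranexamic acid pharmacology) gives oral and intravenous doses and describes the drug's uses. It then says that "it is contraindicated in patients with disseminated intravascular coagulation and upper genitourinary tract bleeding (kidney and ureter"), and gives the reason: "due to its potential to cause excessive blood clot formation". The sentence carries no limit by route or dose.

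The list headed Exclusion criteria has 15 items. The one that refers to the study drug by name is item 2, "Patients who have an allergy to tranexamic acid".

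Under Before surgery, patients are "determined to be eligible for the study based on the inclusion and exclusion criteria through history taking, physical examination". The other sources named there are ECG, enzyme and blood-test findings, taken from the hospital record. Section 3.4 describes consecutive sampling until the target size is reached. The treatment group "received 5 g of tranexamic acid in 50 mL of 0.9% NaCl solution administered topically to the pericardial cavity"; the OPCAB text under Perioperative also gives a 5 g dose.

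**The concern.** Eligibility is settled by the written criteria. If those criteria do not carry over a contraindication that the same document states, a patient can satisfy every entry rule and still be someone to whom the protocol says the drug should not be given. The list has no general item excluding patients with any contraindication to the study drug, and no clause leaving exclusion to the investigator's judgement.

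What is at stake is the safety of an individual patient. The stated hazard is excessive clotting. The listed outcomes (Tables 3.1 and 3.3) are drain volume and transfusion, with nothing on the urinary tract, so the entry criteria are the only written safeguard on this point.

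**Working it through.** No arithmetic bears on this point. The check sets each contraindication named in section 6.3.1 against every place where the protocol could screen it out.

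**Disseminated intravascular coagulation.** Exclusion item 5 covers a history of bleeding disorders (coagulopathy) and gives examples introduced by *such as*. The examples do not name this condition, but the class is open-ended and reasonably includes it. Covered.

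**Bleeding from the kidney or ureter.** The nearest candidates are:

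- Item 2, allergy to the drug: a different condition.
- Item 5, coagulopathy: a kidney or ureter can bleed while clotting is normal.
- Item 6, history of thromboembolic disease: concerns clotting events, not urinary bleeding.
- Item 9, estimated glomerular filtration rate below 30 mL/min or dialysis: concerns kidney function, not bleeding.
- Items 10 and 11, recent antiplatelet or anticoagulant treatment, or a raised INR on warfarin: concern treatment before surgery.
- Item 12, platelets below 50,000 per μL: a laboratory threshold.
- The remaining items (refusal to take part, urgent or minimally invasive surgery, double valve procedure, endocarditis, previous cardiac surgery, pregnancy or breast feeding, refusal of blood products, pericarditis) are unrelated.

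The inclusion criteria do not mention it. The dropout criteria concern leaving theatre on mechanical support and intraoperative resuscitation. The day-before list in Table 3.3 covers consent, stopping certain drugs and recording data. Not covered anywhere.

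Count: two contraindications named, one reasonably covered, one not covered.

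**The patient who passes.** An adult listed for elective surgery who has active bleeding from the kidney or ureter, normal coagulation, a filtration rate of at least 30 mL/min, adequate platelets and no thromboembolic history, and who meets the other entry rules, is eligible as the criteria are written.

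**Does the topical route remove the contraindication?** The protocol offers two pieces of exposure evidence in section 6.3.3:

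- Mean peak serum levels of 4.9 and 5.2 mcg/mL after wound application, against the 10 mcg/mL given in section 6.3.1 as the minimum to inhibit fibrinolysis in vitro. The dose behind these levels is not stated.
- A pericardial study of 1 g in 100 mL, in which the drug was not detected in blood two hours after the chest tube was opened. This trial uses 5 g.

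No level is cited as following 5 g in the pericardium. Nowhere does the protocol say that the contraindication does not apply to topical use.

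**The case against.** The strongest reply is that the hazard lies far from the site of application. Tranexamic acid in the pericardium can affect a bleeding kidney or ureter only through the circulation, and the case for the topical route is that little of the drug gets there. Section 6.3.3 says of the wound-application concentrations: "These levels are lower than the minimum levels required for systemic effects". The contraindication appears in a section whose stated doses are oral and intravenous. On that view, leaving it off the list fits the trial's rationale. This stands in part: the topical route probably lowers the risk. It does not close the gap, because the protocol never makes the argument for this contraindication. The list also keeps thromboembolic history and low filtration rate as exclusions despite the topical route, and sections 6.3.1 and 6.3.2 link those to systemic effects and to elimination of the drug.

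A second reply is that the patient is hypothetical. Urgent and emergency surgery is excluded, so are several bleeding risks, and ordinary preoperative care may well notice overt bleeding. This stands, and it is why the point is minor.

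A third is that a criterion requiring bleeding to be located in the kidney or ureter would need tests that are not planned: the screening text names no urinalysis or urinary imaging. This stands, and the remedy has to be worded to allow for it.

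A reader might go further and infer from the 5 g dose that systemic exposure here will be material, or that all the cited exposure data come from lower doses. The documents support neither. Only the pericardial study has a stated lower dose. A comparison of instilled doses does not measure what reaches the blood, and the missing exclusion would be the same gap at 1 g.

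**Conclusion.** The point holds as a small patient-safety omission. The protocol names a contraindication, does not limit it by route, and has no criterion that screens for it. That rests on comparing the text alone, with one reading assumed: that disseminated intravascular coagulation counts as coagulopathy under item 5. It would therefore be too strong to say that both named contraindications are missing.

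The number of patients affected cannot be worked out, because the documents give no prevalence. In an elective population it is probably none or very few; that is a judgement, not a calculation. The documents do not show that any patient would be harmed.

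Nothing statistical follows. The planned 132 patients (22 per group × 2 groups × 3 types of surgery), the power and the analysis are the same with or without the extra line.

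**What to change.** Add one item to the exclusion criteria: *known or clinically evident active upper urinary tract bleeding (kidney or ureter)*. Check it through the history taking and medical-record review already planned under Before surgery. With this wording no urinalysis or imaging has to be added.

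The cost is one line of text, a marginally narrower population and possibly one patient replaced.

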5.5.2. Dropout criteria

1. Patients are discharged from the operating room with a heart-lung bypass machine or extracorporeal membrane oxygenation (ECMO).
2. History of intraoperative internal or external heart-lung resuscitation.

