5.6. Estimated sample size

The number of samples in this study was calculated twice because the dependent variables observed were the amount of bleeding and the need for postoperative blood transfusion, all of which were numerical variables. From the overall calculation results, the largest sample size for this study was taken, then 10% was added to accommodate the possibility of *dropping out*. The formula used in the sample calculation for both variables is the hypothesis test formula for the mean of two independent groups. The literature used as a reference for calculating the sample of this study is a study by Chaudhary et al. (2018).⁴⁴ The following are the sample calculation results for each research variable.

- **A variable amount of bleeding**

$$n_1 = n_2 = 2 \left[\frac{(z_\alpha + z_\beta)s}{(x_1 - x_2)} \right]^2$$
$$n_1 = n_2 = 2 \left[\frac{(1,96 + 0,842)339,021}{300} \right]^2$$
$$n_1 = n_2 = 20,05 \sim 20 \text{ sample}$$

Description:

= normal standard deviation for type I error with α is 0.05 (1.96)

= normal standard deviation for type II error with β is 0.2 (0.842)

= standard deviation between placebo and treatment groups according to the study (placebo = 445.941 mL and treatment = 232.101 mL, so that the mean value taken = 339.021 mL)⁴⁴

= expected clinical difference (taken 300 mL)

- **Variable blood transfusion needs**

$$n_1 = n_2 = 2 \left[\frac{(z_\alpha + z_\beta)s}{(x_1 - x_2)} \right]^2$$

$$n_1 = n_2 = 2 \left[\frac{(1,96 + 0,842)1,072}{1} \right]^2$$

$$n_1 = n_2 = 18,04 \sim 18 \text{ sample}$$

Description:

= average standard deviation for type I error with α is 0.05 (1.96)

= average standard deviation for type II error with β is 0.2 (0.842)

= standard deviation between placebo and treatment groups according to the study (placebo = 1.225 units and treatment = 0.918 units so that the mean value taken = 1.072 units)⁴⁴

= expected clinical difference (taken as 1 unit)

Based on the above calculation results, 20 patients were taken as the minimum sample size for each placebo and treatment group. With the addition of 10% to anticipate dropouts (2 patients per group), the total sample for each group was 22 samples. The total sample for both groups was 44 patients. In this study, there are three arms group (CABG group, OPCAB group, and Valve Surgery group). The total sample for both arms group was 132 patients.

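### The dropout criteria remove randomised patients for events during or at the end of surgery, and no as-randomised analysis is planned

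*Combined protocol and SAP*

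**What the plan says.** - **Randomisation.** Section 3.7.1 (Before surgery) says that consenting patients "were randomized into treatment or control (placebo) groups".
- **Study solution.** It is given late in the operation: "administered topically to the pericardial cavity after protamine administration and before sternotomy closure" in section 3.7.1 and, for on-pump surgery, "after the heart-lung bypass machine stopped and before the sternum was closed" in section 3.7.2.
- **Dropout.** Section 5.5.2 has two criteria: "Patients are discharged from the operating room with a heart-lung bypass machine or extracorporeal membrane oxygenation (ECMO") and "History of intraoperative internal or external heart-lung resuscitation". The second has no time limit relative to the solution.
- **Sample size.** Section 5.6 takes 20 per group as the minimum and continues: "With the addition of 10% to anticipate dropouts (2 patients per group"), which gives 22 per group in each surgery group and 132 in total.
- **Analysis.** Section 3.12 names the t-test and the Mann-Whitney test. It defines no analysis population and does not say how the outcomes of dropouts are handled. The dummy results tables show n = 22 in every group.

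**The concern.** Randomisation makes the two arms comparable as allocated. Both dropout criteria are met later, by patients who are likely to be among the sickest and may be among the heaviest bleeders. Some of these events can follow the study solution: resuscitation after instillation, or mechanical support started before the patient leaves the operating room. Such events may be related to bleeding, which is the outcome. They may also be related to treatment, since sections 1.1 and 6.3.2 themselves raise a theoretical risk of graft or coronary occlusion and myocardial infarction with tranexamic acid.

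If treatment or outcome influences who is removed, the patients left in each arm are no longer comparable, and the bleeding and transfusion differences can be biased in either direction. With 22 patients per arm, one or two removals are enough to move a mean. The silence on the analysis set is a further problem, because it leaves the handling of these patients to be settled after the data are seen.

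**Working it through.** **1. The plan's own figures (section 5.6).** The inputs are z = 1.96 ("normal standard deviation for type I error with α is 0.05 (1.96")), z = 0.842, SD 339.021 mL and a difference of 300 mL.

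n = 2 × [(1.96 + 0.842) × 339.021 / 300]² = 20.05, stated as 20. Then 20 × 1.10 = 22, and 22 × 2 × 3 = 132. The figures reproduce. Adding patients above a stated minimum makes sense only if dropouts do not count towards that minimum. This is the textual basis for inferring removal.

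**2. Order of events.**

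| Event | Where it falls |
|---|---|
| Randomisation | Before surgery |
| Resuscitation (criterion 2) | Any time during surgery, before or after the solution |
| Study solution | Late in surgery, before sternal closure |
| Leaving the operating room on bypass or ECMO (criterion 1) | Recorded at exit; the cause may come before or after the solution |

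Every exclusion under section 5.5.2 is therefore post-randomisation. Only some are post-solution.

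**3. Size of a one-sided removal (illustration).** The documents give no event rate and no drain volume for these patients. Assume that k of 22 patients are removed from one arm and that they bled E mL more than the patients who remain. The full-arm mean is the remaining mean plus kE/22, so removal lowers the arm mean by kE/22.

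| k | E = 500 | E = 1,000 | E = 1,500 |
|---|---|---|---|
| 1 | 22.7 mL | 45.5 mL | 68.2 mL |
| 2 | 45.5 mL | 90.9 mL | 136.4 mL |

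As a share of the 300 mL target, k = 2 gives 45.5/300 = 15%, 90.9/300 = 30% and 136.4/300 = 45%. The choice k = 2 borrows the general dropout allowance and is not an estimate of how often these events occur.

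**4. Equal against unequal removal.** A simulation used 20,000 runs, normal data with SD 339.021, no drug effect, and two such patients in each arm of 22, analysed with a two-sided t-test at 5%.
- Two removed from each arm: type I error about 5% (5.0, 4.9 and 4.9% for E = 500, 1,000 and 1,500).
- Two removed from one arm and none from the other: 5.9, 7.3 and 7.9%.

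The distortion comes from imbalance, not from exclusion as such.

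**5. Power.** Using power = Φ(300 / [SD × √(2/n)] − 1.96) with the SD held at 339.021:
- n = 22: 300/(339.021 × 0.3015) = 2.935, power 83.5%.
- n = 20: 300/(339.021 × 0.3162) = 2.798, power 79.9%.

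The SD would not stay fixed if extreme patients are kept. With k such patients per arm, the variance rises by (k/22)(1 − k/22)E².
- k = 1, E = 500: SD = √(339.021² + 10,847) = 355 mL, power 80.1% with n = 22.
- k = 2, E = 1,500: SD = √(339.021² + 185,950) = 549 mL, power 44% for a t-test.

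Keeping everyone is therefore nearly free if such patients are few and moderately extreme, but not at the top of the assumed range.

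**The case against.** The strongest reply is that the solution comes so late that many of these events will precede it. Resuscitation can happen at any earlier stage, and a patient who cannot be weaned may never reach the point where the solution is due. Such events cannot be caused by the drug. The criteria are also fairly objective, they apply to both arms, and section 3.7.1 says that "neither the researchers nor the patients were aware of the preparations used intraoperatively". Removal should then balance in expectation, and the simulation confirms that equal removal leaves the type I error near 5%. The pattern of two removed against none, with two such patients in each arm, is also not what a uniformly applied rule would produce.

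Much of this stands. A reader might infer from section 5.5.2 that both criteria are met at or after administration; the text does not support that. A reader might also take the 30 to 45 minutes in section 3.7.2 as the time from instillation to skin closure. It runs from sternal closure to skin suturing, and in OPCAB the fluid is left for five minutes and cleared before closure.

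What does not stand is the step to no concern. The rule is not confined to events before the solution. Blinding prevents selective application of the rule, but it does not help if treatment or bleeding itself causes the event that triggers removal. Balance in expectation also does not guarantee balance among 22 per arm.

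Two further limits are fair. The 500 to 1,500 mL excess has no source in the documents. And where the data are not normal the plan uses the Mann-Whitney test, for which a shift in means is only a rough guide.

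**Conclusion.** The point holds as a post-randomisation exclusion with no defined analysis set. Both criteria can only be met after randomisation, and no as-randomised analysis is planned. Removal from the analysis is a fair inference from the dropout label and the 10% allowance. A reader might take it as stated text, but it is not, and the dummy tables with n = 22 point the other way. That conflict itself needs resolving.

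Bias arises only if removals differ between arms in number or in prognosis. The illustrative shift is 23 to 68 mL for one patient, and 45 to 136 mL (15 to 45% of the target) for two patients from one arm only. It rests on the assumed excess of 500 to 1,500 mL over the remaining patients. A reader might conclude that the trial's result will be biased, or that its type I error is 7.9%. Neither follows, because the documents give no rate, no volume and no sign of imbalance. The change is worth making because it removes an avoidable risk and an ambiguity at low cost.

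**What to change.** 1. In sections 5.5.2 and 3.12, state that the primary analysis includes all randomised patients in their allocated arm, within each surgery group, using drain and transfusion data as recorded.
2. In section 3.7.3 and Table 3.3, state that these data continue to be collected for patients who meet a section 5.5.2 criterion.
3. Report by arm the number meeting each criterion, the timing relative to the study solution, and the reason.
4. Use the set without these patients, or without those who never received solution (decided blind to arm), only as a sensitivity analysis.
5. Make the group sizes in the dummy tables agree with the analysis set.

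The cost is wording and a little more data collection, and the planned 22 per group already covers it. The statistical downside is larger variance from a few extreme patients. It is slight if they are rare and moderately extreme, and greater towards the top of the range shown. The sensitivity analysis will show how far the result depends on them.
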